4.1.2 Part 2 – Dose Expansion

Upon completion of Part 1 of the study, the dose expansion phase will begin at the OBD/MSBED and drug administration schedule with the intention of confirming the safety and tolerability and determining the efficacy of AMG 176 in combination with azacitidine in not only R/R HR- MDS/CMML, but also in frontline HR-MDS/CMML. An additional 60 subjects will be enrolled in Part 2 of the study as follows:

HMA Failure Cohort: stratified by venetoclax exposure history

○ HMA Failure, venetoclax-Naïve (n = 20)

DLT = dose limiting toxicity.

^a A subject is considered DLT-evaluable if he/she experienced a DLT during the DLT evaluation period; or if he/she received 75% of the planned doses of AMG 176 and 100% of the planned doses of azacitidine, and completed the DLT evaluation period.

^b De-escalate guideline applies only when current dose level and enrollment is allowed to a lower dose level.

^c The maximum number of evaluable subjects at one dose level is 10.

Protocol Number: 20200392

Date: 28 April 2022 Page 42 of 149

- HMA Failure, venetoclax-Exposed (n = 20)
- Newly Diagnosed (n = 20) subjects will not be enrolled into this cohort until all previous cohorts have been completed and the data reviewed by the FDA.
 Toxicity will be monitored for each cohort using a Bayesian approach proposed by Thall, Simon, and Estey (1995).

The incidence of grade 3 or higher treatment-related non-hematological adverse events will be evaluated once every 5 subjects have had the chance to receive at least 1 cycle of treatment at the determined dose level for Part 2. Assuming a prior distribution of beta (1, 1), if the posterior probability that the incidence is greater than 20% is > 80% at these interim analyses, the study will stop early. The purpose of the safety interim analyses is to assess if the threshold for early termination has been reached. The stopping rules and operating characteristics are described in Table 4-2 and Table 4-3.

Number of subjectsStop study if observing this number of subjects with grade 3 or higher treatment-related non-hematological adverse event $5 \sim 6$ ≥ 2 $7 \sim 10$ ≥ 3 $11 \sim 14$ ≥ 4 $15 \sim 19$ ≥ 5 20Completes

Table 4-2. Stopping Boundary for Each Cohort in Part 2

| Table 4-3. O | perating | Characte | ristics | in | Part 2 |
|--------------|----------|----------|---------|----|--------|
|--------------|----------|----------|---------|----|--------|

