| True grade 3 or higher treatment-related non-hematological adverse event rate | Probability of early stopping |
|---|-------------------------------|
| 0.10 | 15% |
| 0.15 | 32% |
| 0.20 | 51% |
| 0.25 | 69% |
| 0.30 | 82% |

Duration of Therapy

In the absence of treatment delays due to clinically significant study drug-related adverse events, treatment may continue until one of the following criteria applies:

- Clinically significant progressive disease. Subjects may continue therapy with either
 or both AMG 176 and azacitidine as long as they have stable disease, as long as, in
 the opinion of the treating physician and/or Principal Investigator (PI), the subject
 continues to derive clinical benefit and has otherwise not had an event requiring
 permanent discontinuation.
- Inter-current illness that prevents further administration of treatment.

Protocol Number: 20200392

Date: 28 April 2022 Page 43 of 149

Subject decides to withdraw from the study.

• Excess toxicity that in the opinion of the PI would present a safety risk for further participation on the study.

Subjects may receive further courses of therapy not earlier than 4 weeks from the previous course, provided the subject has recovered from myelosuppression considered to be related to chemotherapy.

A minimum of one full course (or 4 weeks from the start of therapy) will be required for a subject to be considered as having received an adequate trial to evaluate efficacy. All subjects receiving at least one dose of any of the two drugs will be considered evaluable for toxicity. Subjects achieving a partial remission or with stable disease may continue on therapy until definite evidence of disease progression.

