5.1 Inclusion Criteria

Subjects are eligible to be included in the study only if all of the following criteria apply:

- 101 Age \geq 18 years of age.
- Eastern Cooperative Oncology Group (ECOG) performance status of 0 to 2. Refer to Section 11.11.1 for more details.
- For Part 1, patients have R/R MDS post-HMA failure, defined as prior receipt of 4 cycles of HMA therapy (including but not limited to decitabine, azacitidine, investigational HMAs such as SGI-110, and oral HMAs such as ASTX727 and CC-486) with failure to attain a response or progression of disease or relapse at any time after prior response to HMA therapy.

Note:

Protocol Number: 20200392

Date: 28 April 2022 Page 45 of 149

1) Patients with HR-CMML (CMML, CMML-1 or 2 by World Health Organization [WHO]) are eligible.

- 2) Hydroxyurea administration will be allowed on the study to lower the white cell count to $\leq 10\,000/\mu L$ prior to the initiation of therapy.
- 104 For Part 2, patients will be divided into 2 cohorts:
 - a. HMA Failure Cohort: patients with R/R MDS post-HMA failure (defined as prior receipt of 4 cycles of HMA therapy with failure to attain a response or progression of disease or relapse at any time after prior response to HMA therapy) are eligible. Patients who have previously received venetoclax are eligible and will be stratified accordingly in the HMA Failure Cohort.
 - **b.** Newly Diagnosed Cohort: patients with treatment-naïve newly diagnosed HR-MDS (IPSS score ≥ 3.5) are eligible.

Note

- 1) Patients with HR-CMML (CMML-1 or 2 by WHO) are eligible.
- 2) Hydroxyurea administration will be allowed on the study to lower the white cell count to $\leq 10\,000/\mu L$ prior to the initiation of therapy.
- 3) Patients who have previously received venetoclax are eligible and will be stratified accordingly in the HMA Failure Cohort.
- 105 Must be willing and able to undergo bone marrow aspirate at screening.
- Life expectancy of > 3 months, in the opinion of the investigator.
- Hepatic function, as follows: AST, and Alanine Aminotransferase (ALT) < 3 X ULN, total bilirubin < 1.5 X ULN (except subjects with Gilbert's syndrome).
- 108 Cardiac function, as follows; Left Ventricular Ejection Fraction (LVEF) > 50% 2D transthoracic ECHO is the preferred method of evaluation. Multigated Acquisition (MUGA) scan is acceptable if ECHO is not available.

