#### Part 2 – Dose Expansion (Not Applicable, did not enroll)

Upon completion of Part 1 of the study, the dose expansion phase will begin at the **OBD/MSBED** and drug administration schedule with the intention of confirming the safety and tolerability and determining the efficacy of AMG 176 in combination with azacitidine in not only R/R HR- MDS/CMML, but also in frontline HR-MDS/CMML. An additional 60 subjects will be enrolled in Part 2 of the study as follows:

- HMA Failure Cohort: stratified by venetoclax exposure history
  - HMA Failure, venetoclax-Naïve (n = 20)
  - HMA Failure, venetoclax-Exposed (n = 20)
- Newly Diagnosed (n = 20) subjects will not be enrolled into this cohort until all previous cohorts have been completed and the data reviewed by the FDA.
   Toxicity will be monitored for each cohort using a Bayesian approach proposed by Thall, Simon, and Estey (1995).

The incidence of grade 3 or higher treatment-related non-hematological adverse events will be evaluated once every 5 subjects have had the chance to receive at least 1 cycle of treatment at the determined dose level for Part 2. Assuming a prior distribution of beta (1, 1), if the posterior probability that the incidence is greater than 20% is > 80% at these interim analyses, the study will stop early. The purpose of the safety interim analyses is to assess if the threshold for early termination has been reached. The stopping rules and operating characteristics are described in Protocol Table 3-2 and Table 3-3.

Table 3-2. Stopping Boundary for Each Cohort in Part 2

Number of subjects	Stop study if observing this number of subjects with grade 3 or higher treatment-related non-hematological adverse event
5 ~ 6	≥ 2

<sup>a A subject is considered DLT-evaluable if he/she experienced a DLT during the DLT evaluation period; or if he/she received 75% of the planned doses of AMG 176 and 100% of the planned doses of azacitidine and completed the DLT evaluation period.

<sup>b De-escalate guideline applies only when current dose level and enrollment is allowed to a lower dose level.

<sup>c The maximum number of evaluable subjects at one dose level is 10.

Protocol Number: 20200392

Date: 10 May 2024 Page 15 of 33

7 ~ 10	≥ 3
11 ~ 14	≥ 4
15 ~ 19	≥ 5
20	Completes

Table 3-3. Operating Characteristics in Part 2

True grade 3 or higher treatment-related non-hematological adverse event rate	Probability of early stopping
0.10	15%

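### The Part 2 toxicity boundary is set per cohort but stops the study, and Table 4-3 matches neither that stopping unit nor the stated look every 5 subjects

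*Protocol*

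**What the plan says.** Protocol 4.1.2 enrolls 60 subjects in Part 2, in three groups of 20: HMA failure venetoclax-naïve, HMA failure venetoclax-exposed, and newly diagnosed. It states that toxicity is monitored for each cohort and evaluated once every 5 subjects have had the chance to receive a cycle of treatment. With a Beta(1,1) prior, the rule is: "if the posterior probability that the incidence is greater than 20% is > 80% at these interim analyses, the study will stop early".

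The boundaries are titled "Table 4-2. Stopping Boundary for Each Cohort in Part 2". They are at least 2 events at n = 5–6, 3 at 7–10, 4 at 11–14 and 5 at 15–19, with the cohort complete at 20. The column heading of that table also names the study as what stops. Table 4-3 has one result column, "Probability of early stopping", which carries no unit and no look schedule.

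SAP 3.1 repeats the rule and both tables ("Table 3-2. Stopping Boundary for Each Cohort in Part 2") under a heading that marks Part 2 as not enrolled. Protocol 5.1, criterion 104, counts differently: "For Part 2, patients will be divided into 2 cohorts", with HMA failure as one cohort stratified by venetoclax history.

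**The concern.** A stopping rule has to say what stops and when it is checked, and its operating characteristics have to describe that event on that schedule. Here the boundary belongs to a cohort, the consequence belongs to the study, and the table does not say which it describes. If any cohort's crossing ends the study, three chances to cross make a false stop of a tolerable regimen more likely than a single-cohort table shows. A stop in either HMA-failure group would also keep the newly diagnosed cohort from opening. If only the cohort stops, the question is whether the printed figures fit the looks that would actually be made, because they are the stated chance of catching a toxic regimen.

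**Working it through.** **Inputs.** Prior Beta(1,1); criterion Pr(rate > 0.20 | data) > 0.80; cohort maximum 20; looks every 5 subjects, so n = 5, 10, 15 before completion; three groups of 20 (all Protocol 4.1.2).

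**Step 1: boundaries.** With x events in n subjects, the posterior is Beta(1 + x, 1 + n − x). The boundary is the smallest x for which its mass above 0.20 exceeds 0.80. For example, 1/5 gives 0.655 and 2/5 gives 0.901; 2/7 gives 0.797 and 3/7 gives 0.944; 4/15 gives 0.798 and 5/15 gives 0.918. Table 4-2 is reproduced exactly for every n from 5 to 19.

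**Step 2: reproduce Table 4-3.** An exact binomial recursion carries the event count forward from look to look and removes the paths that cross. For one cohort of 20 with a look after every subject from 5 to 19, it gives 15.0/32.0/51.3/68.9/82.3%, which is Table 4-3.

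**Step 3: the schedule in the text.** The same recursion with looks at 5, 10 and 15 can be checked by hand at a true rate of 0.10:

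- n = 5, at least 2 events: 1 − 0.59049 − 0.32805 = 0.08146.
- n = 10, at least 3 events: from 0 events at n = 5, 0.59049 × 0.00856; from 1 event, 0.32805 × 0.08146. The sum is 0.03178.
- n = 15, at least 5 events: the surviving counts 0, 1, 2 at n = 10 have probabilities 0.34868, 0.38742, 0.15066. They need at least 5, 4, 3 more events in five subjects, with probabilities 0.00001, 0.00046, 0.00856. The sum is 0.00147.
- Total: 0.08146 + 0.03178 + 0.00147 = 0.1147.

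**Step 4: study level.** If crossing in any of three cohorts stops the study, and the cohorts are independent with a common true rate, P(study stops) = 1 − (1 − p)³, with p the single-cohort probability. At 0.10 on the stated looks this is 1 − 0.8853³ = 0.306. With a look after every subject it is 1 − 0.8503³ = 0.385.

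| True rate | Table 4-3 as printed | One cohort, looks at 5, 10, 15 | Any of three cohorts, looks at 5, 10, 15 | Any of three cohorts, look after every subject |
|---|---|---|---|---|
| 0.10 | 15% | 11.5% | 30.6% | 38.5% |
| 0.15 | 32% | 24.8% | 57.4% | 68.6% |
| 0.20 | 51% | 40.5% | 78.9% | 88.5% |
| 0.25 | 69% | 56.3% | 91.6% | 97.0% |
| 0.30 | 82% | 70.3% | 97.4% | 99.4% |

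On the stated looks, the ratio of the three-cohort figure to the printed one is 30.6/15 = 2.04, 57.4/32 = 1.79, 78.9/51 = 1.55, 91.6/69 = 1.33 and 97.4/82 = 1.19.

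**The case against.** The strongest reply is that Table 4-3 is a sound per-cohort calculation and that the study was written where the cohort was meant. On that reading the table is on the right scale and only a noun needs changing. This stands in part: the documents do not settle which was meant, and the study-level figures apply only if the wording is taken as written. But the study is named twice, in the text and in the Table 4-2 column heading. Changing the noun would also leave the look schedule wrong: per cohort, the printed figures are 3.5 to about 12 percentage points above what looks every 5 subjects deliver.

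The reply can also cite Table 4-2, which lists a boundary for every n from 5 to 19, as a sign that continuous monitoring was intended. That is possible, and the printed figures agree with it, but the text says otherwise and the two must be reconciled.

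The multiplicity result is also fairly challenged. The documents state neither independence nor a common rate across HMA-failure and newly diagnosed subjects. Positive dependence would lower the study-level figures, down to the single-cohort figure if the cohorts always crossed together. Counting only the two HMA-failure groups on the stated looks gives 1 − 0.8853² = 21.6% at a rate of 0.10.

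Three stronger readings are tempting but not supported:

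- A reader might infer that the table understates study stopping by a factor of two or more at any acceptable rate. On the table's own look basis that holds at 0.10 (2.6) and 0.15 (2.1), but at 0.20 the factor is 1.7. On the stated looks it is 2.0, 1.8 and 1.55.
- A reader might take criterion 104 to mean one HMA-failure cohort of 40, leaving subjects 21–40 without a boundary. Section 4.1.2 lists groups of 20 and Table 4-2 ends at 20, so the count in criterion 104 is better read as an eligibility grouping.
- A reader might see a missing boundary at n = 20. By then that group's accrual is complete, and FDA data review is already required before the newly diagnosed cohort opens. With a look after every subject, a cohort that passes n = 19 has at most 4 events and cannot reach the 6 that the criterion would require at 20. A boundary there is a design choice, not a correction.

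**Conclusion.** The point holds as an inconsistency between the rule and its stated operating characteristics. Table 4-3 describes one cohort of 20 monitored after every subject; the text describes a look every 5 subjects and a study-wide stop. On the stated looks, the printed 15% at a true rate of 0.10 should be 11.5% if a cohort stops, or 30.6% if any of three cohorts stops the study. The printed 82% at 0.30 should be 70.3% or 97.4%. So the table overstates detection of a toxic regimen on one reading and understates false stopping on the other.

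The single-cohort figures rest only on the documents' prior, criterion and looks. The three-cohort figures also assume independence, a common rate and three monitored groups. The importance is limited: the SAP marks Part 2 as not enrolled and records early termination, so the rule was never applied and no decision or result depends on it.

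**What to change.** In Protocol 4.1.2 and SAP 3.1:

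- Reconcile monitoring for each cohort with the statement that "the study will stop early", in both the text and the Table 4-2 column heading, so that the rule says what a crossing stops.
- State that the three groups of 20 are the monitored units, and align the cohort count in criterion 104 with that.
- Reconcile the look schedule: the text has looks every 5 subjects, while Table 4-2 lists every n from 5 to 19.
- Recompute Table 4-3 (SAP Table 3-3) for the chosen unit and schedule, and put both in its title. If study-level figures are shown, state the independence and common-rate assumptions beside them.

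The cost is wording and one recomputed table, with no added subjects. Since Part 2 did not enroll, a short clarification in the SAP or study report would suffice for this trial. The full correction matters if the rule is reused.

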4.2 Patient Input into the Study Design

The overall study design is described by a study schema in Section 1.2. The endpoints are defined in Section 3.

Approximately 120 subjects will be enrolled in the study, with up to 60 subjects in Part 1 and up to 60 subjects in Part 2.

Subjects in this clinical investigation shall be referred to as "subjects". For the sample size justification, see Section 9.2.

4.3 Justification for Dose

4.3.1 Justification for Investigational Product Dose

The starting dose of AMG 176 will be 120 mg/m² QW, which is based on prior clinical experience that demonstrated significant clinical safety and efficacy in subjects with AML (Section 2.2.2.4). Increased troponin is an identified risk with AMG 176 (Section 2.3.2). Troponin elevations in AML and MM subjects studied to date (Study 20150161) were reported primarily at higher dose levels of AMG 176 of 360 and 480 mg/m² as monotherapy when administered twice weekly using high sensitivity assays (Abbott Architect hs-cTnI) but were not observed for dose levels of 120 and 180 mg/m² administered weekly on a 3 out of 4 week dosing schedule. Additionally, AMG 176 was well-tolerated with no DLTs reported in subjects treated with 120 mg/m² monotherapy and 60 mg/m² in combination with azacitidine when administered weekly for 4 consecutive weeks each cycle. In this study, AMG 176 will be administered QW for 4 consecutive weeks each cycle. This 28-day duration is considered 1 cycle. Lead in dosing of 120 mg/m² will be utilized whenever the target dose level is at 180 mg/m² or higher.

Protocol Number: 20200392

Date: 28 April 2022 Page 44 of 149

4.3.2 Justification for Non-investigational Product Dose

The dose of azacitidine for the first treatment cycle, for all subjects regardless of baseline hematology laboratory values, is 75 mg/m² subcutaneously or intravenously, daily for the first 7 days of a 4-week cycle (as per local prescribing information). Prophylactic treatment to mitigate nausea and vomiting will be administered.

4.4 End of Study

An individual subject is considered to have completed the study if he/she has completed the last visit or the last scheduled procedure shown in the Schedule of Activities. The total study duration for an individual subject is 7.5 months from screening through the safety follow-up visit.

The end of study (EOS) date is defined as the date when the last subject across all sites is assessed or receives an intervention for evaluation in the study (ie, last subject last visit), including any additional parts in the study (eg, long-term follow-up, additional antibody testing), as applicable.

5. Study Population

Investigators will be expected to maintain a screening log of all potential study candidates that includes limited information about the potential candidate (eg, date of screening).

Eligibility criteria will be evaluated during screening.

Before any study-specific activities/procedures, the appropriate written informed consent must be obtained (see Section 11.3).

Prospective approval of protocol deviations to recruitment and enrollment criteria, also known as protocol waivers or exemptions will not be provided.

5.1 Inclusion Criteria

Subjects are eligible to be included in the study only if all of the following criteria apply:

- 101 Age \geq 18 years of age.
- Eastern Cooperative Oncology Group (ECOG) performance status of 0 to 2. Refer to Section 11.11.1 for more details.
- For Part 1, patients have R/R MDS post-HMA failure, defined as prior receipt of 4 cycles of HMA therapy (including but not limited to decitabine, azacitidine, investigational HMAs such as SGI-110, and oral HMAs such as ASTX727 and CC-486) with failure to attain a response or progression of disease or relapse at any time after prior response to HMA therapy.

Note:

Protocol Number: 20200392

Date: 28 April 2022 Page 45 of 149

1) Patients with HR-CMML (CMML, CMML-1 or 2 by World Health Organization [WHO]) are eligible.

- 2) Hydroxyurea administration will be allowed on the study to lower the white cell count to $\leq 10\,000/\mu L$ prior to the initiation of therapy.
- 104 For Part 2, patients will be divided into 2 cohorts:
 - a. HMA Failure Cohort: patients with R/R MDS post-HMA failure (defined as prior receipt of 4 cycles of HMA therapy with failure to attain a response or progression of disease or relapse at any time after prior response to HMA therapy) are eligible. Patients who have previously received venetoclax are eligible and will be stratified accordingly in the HMA Failure Cohort.
 - **b.** Newly Diagnosed Cohort: patients with treatment-naïve newly diagnosed HR-MDS (IPSS score ≥ 3.5) are eligible.

Note

- 1) Patients with HR-CMML (CMML-1 or 2 by WHO) are eligible.
- 2) Hydroxyurea administration will be allowed on the study to lower the white cell count to $\leq 10\,000/\mu L$ prior to the initiation of therapy.
- 3) Patients who have previously received venetoclax are eligible and will be stratified accordingly in the HMA Failure Cohort.
- 105 Must be willing and able to undergo bone marrow aspirate at screening.
- Life expectancy of > 3 months, in the opinion of the investigator.
- Hepatic function, as follows: AST, and Alanine Aminotransferase (ALT) < 3 X ULN, total bilirubin < 1.5 X ULN (except subjects with Gilbert's syndrome).
- 108 Cardiac function, as follows; Left Ventricular Ejection Fraction (LVEF) > 50% 2D transthoracic ECHO is the preferred method of evaluation. Multigated Acquisition (MUGA) scan is acceptable if ECHO is not available.
- Calculated or measured Creatinine Clearance (CrCl) of ≥ 30 mL/minute calculated using the formula of Cockcroft and Gault ([140 Age × Mass kg] / [72 × Creatinine mg/dL]). Multiply result by 0.85 if female.
- 110 Females must be surgically or biologically sterile or postmenopausal (amenorrheic for at least 12 months) or if of childbearing potential, must have a negative serum or urine pregnancy test within 72 hours before the start of the treatment. Female subjects of childbearing potential must agree to use highly effective methods of contraception (see Section 11.5) an adequate method of contraception during treatment and until 3 months after the last treatment.
- Males must be surgically or biologically sterile or agree to use an adequate method of contraception during the study until 3 months after the last treatment.

5.2 Exclusion Criteria

Subjects are excluded from the study if any of the following criteria apply:

Disease Related

- 201 Patients with newly diagnosed MDS with IPSS-R lower-risk category (IPSS score <3.5).
- 202 Patients with CMML-0 by WHO.

Other Medical Conditions

Protocol Number: 20200392

Date: 28 April 2022 Page 46 of 149

- 203 Myocardial infarction within 6 months of enrollment
- 204 Moderate to severe heart failure (New York Heart Association [NYHA] Functional Classification III, IV at baseline).
- 205 History of other malignancy within the past 2 years prior to enrollment, with the following exceptions:
 - Malignancy treated with curative intent and with no known active disease present for ≥ 2 years before enrollment and felt to be at low risk for recurrence by the treating physician.
 - Adequately treated non-melanoma skin cancer or lentigo maligna without evidence of disease.
 - Adequately treated cervical carcinoma in situ without evidence of disease.
 - Adequately treated breast ductal carcinoma in situ without evidence of disease.
 - Prostatic intraepithelial neoplasia without evidence of prostate cancer.
 - Adequately treated urothelial papillary noninvasive carcinoma or carcinoma in situ.
- 206 History of arterial thrombosis (eg, stroke or transient ischemic attack) in the past 6 months prior to enrollment.
- 207 Active infection requiring IV anti-infective treatments within 1 week of enrollment.
- 208 Known or suspected Human Immunodeficiency Virus (HIV) infection or subjects who are HIV seropositive. Testing will be performed if required by local regulatory authorities.
- 209 Patient has chronic respiratory disease that requires continuous oxygen, or significant history of renal, neurologic, psychiatric, endocrinologic, metabolic, or immunologic condition.
- 210 Exclusion of hepatitis B and C infection based on the following results:
 - Positive for Hepatitis B Surface Antigen (HbsAg) (indicative of chronic hepatitis B or recent acute hepatitis B)
 - Negative HbsAg and positive for Hepatitis B Core Antibody (HbcAb) and/or hepatitis B surface antibody: hepatitis B virus DNA by polymerase chain reaction (PCR) is necessary. Detectable hepatitis B virus DNA suggests occult hepatitis B. Negative for PCR test can be enrolled in the study.
 - Positive Hepatitis C Virus Antibody (HCVAb): hepatitis C virus RNA by PCR is necessary. Detectable hepatitis C virus RNA suggests chronic hepatitis C. Negative for PCR test can be enrolled in the study.

Prior/Concomitant Therapy

- 211 Treatment with medications known to cause corrected QT Interval (QTc) interval prolongation within 1 week prior to enrollment unless approved by the Amgen Medical Team.
- Anti-tumor therapy: chemotherapy within 14 days (or 5 half-lives, whichever is shorter) of enrollment, antibody therapy, molecular targeted therapy, or investigational agent within 21 days (or 5 half-lives, whichever is shorter) of

Protocol Number: 20200392

Date: 28 April 2022 Page 47 of 149

enrollment. Exceptions: hydroxyurea to control peripheral blood leukemic cell counts is allowed until prior to receiving the first dose of AMG 176.

- 213 Prior systemic radiation therapy must have been completed at least 28 days prior to enrollment. Prior focal radiotherapy completed at least 14 days prior to enrollment.
- Patient has received a live attenuated vaccine within 4 weeks prior to the first dose of study drug. Patients who have received coronavirus disease 2019 (COVID-19) vaccine within **14** days prior to dosing, or plan to receive a COVID-19 vaccine within 28 days postdose; from 29 days postdose through EOS, vaccination for COVID-19 may be deemed acceptable for a subject following discussion and agreement between the sponsor and the investigator.
- Use of any medications (except anti-tumor medications), including herbal medicines (eg, St. John's wort), vitamins, or supplements consumed by the subject within the 30 days prior to enrollment, and continuing use if applicable, that was not reviewed and approved by the PI and the Amgen Medical Monitor prior to enrollment. Written documentation of this review and Amgen acknowledgment is required for subject participation.
- Use of known strong inhibitors of CYP3A4/P-gp within the 14 days or 5 half-lives (whichever is longer) or products containing grapefruit juice, Seville oranges, or St. John's wort within 7 days, prior to enrollment unless reviewed and approved by the principal investigator and the Amgen medical monitor prior to enrollment. Written documentation of this review and Amgen acknowledgment is required for subject participation.
- Use of known CYP3A4 sensitive substrates with a narrow therapeutic window within 5 half-lives of the drug or its major active metabolite, whichever is longer, following the last dose of the drug prior to receiving the first dose of AMG 176 unless reviewed and approved by the principal investigator and the Amgen medical monitor prior to enrollment. Written documentation of this review and Amgen acknowledgment is required for subject participation. Refer to prescribing information for any concomitant medications.
- 218 Use of known OATP1B1 and/or OATP1B3 or BCRP substrates with a narrow therapeutic window within 5 half-lives of the drug or its major active metabolite, whichever is longer, following the last dose of the drug prior to enrollment unless reviewed and approved by the principal investigator and the Amgen Medical Monitor prior to enrollment. Written documentation of this review and Amgen acknowledgment is required for subject participation. Refer to prescribing information for any concomitant medications.
- 219 Major surgery within 28 days of enrollment.

Prior/Concurrent Clinical Study Experience

Currently receiving treatment in another investigational device or drug study, or less than 30 days since ending treatment on another investigational device or drug study(ies). Other investigational procedures while participating in this study are excluded.

Diagnostic Assessments

Subjects with elevated cardiac troponin above the manufacturer's 99th percentile upper reference limit for ADVIA Centaur XP TnI assay at screening performed by the central laboratory.

Protocol Number: 20200392

Date: 28 April 2022 Page 48 of 149

Subjects with evidence of recent cardiac injury at screening based on Creatine Kinase-Muscle/Brain (CK-MB), N-Terminal Prohormone of Brain Natriuretic Peptide (NT-pro BNP), and Electrocardiogram (ECG) assessments at screening.

Patient has a white blood cell count > 10×10^9 /L. Hydroxyurea or leukapheresis are permitted to meet this criterion.

Other Exclusions

- Female subjects of childbearing potential unwilling to use highly effective methods of contraception (see Section 11.5) during treatment and for an additional 3 months after the last dose of investigational product.
- Female subjects who are breastfeeding or who plan to breastfeed while on study through 3 months after the last dose of investigational product.
- Female subjects planning to become pregnant while on study through 3 months after the last dose of investigational product.
- Female subjects of childbearing potential with a positive pregnancy test assessed at Screening and/or day 1 by a highly sensitive urine or serum pregnancy test.
- Male subjects with a female partner of childbearing potential who are unwilling to practice sexual abstinence (refrain from heterosexual intercourse) or use contraception during treatment and for an additional 4 months after the last dose of investigational product. Refer to Section 11.5 for additional contraceptive information.
- 229 Male subjects with a pregnant partner who are unwilling to practice abstinence or use a condom during treatment and for an additional 4 months after the last dose of investigational product.
- Male subjects unwilling to abstain from donating sperm during treatment and for an additional 4 months after the last dose of investigational product.
- Subject is fit and deemed eligible by the investigator for intensive salvage therapy.
- 232 Subject is eligible for HSCT.
- Subject has known sensitivity to any of the products or components to be administered during dosing.
- Subject likely to not be available to complete all protocol-required study visits or procedures, and/or to comply with all required study procedures (eg, Clinical Outcome Assessments) to the best of the subject and investigator's knowledge.
- History or evidence of any other clinically significant disorder, condition, or disease (with the exception of those outlined above) that, in the opinion of the investigator or Amgen physician, if consulted, would pose a risk to subject safety or interfere with the study evaluation, procedures, or completion.

